We propose a single-center, randomized cross-over study design. The study will be approved by the Mayo Clinic Institutional Review Board, and a consent form will be signed by each participant. We will enroll 100 patients at Mayo Clinic, Rochester, Minnesota, who have LVEF of 35% to 50%. Of these patients, 30 will be women. Participants will undergo placement of a CRT-pacemaker (CRT-P) after the completion of the baseline assessment if all inclusion and none of the exclusion criteria are met. Participants who have an ICD in place, or who meet clinical indication for an ICD, will undergo placement of a CRT-defibrillator (CRT-D). Defibrillation will not be added for patients who do not have an existing ICD system or do not meet clinical indications for an ICD. Participants who have a successful CRT implantation will be randomly assigned 1:1 to have the CRT programmed on (CRT-ON, treatment group) or off (CRT-OFF, control group) within 7 days of completing the implant procedure. Participants will be randomly assigned using an allocation method defined by a biostatistician. Investigators managing HF in study participants will be blinded to the randomization method to minimize potential bias. A washout period after the device implantation will not be used in this study.¹⁹ At 6-month follow-up, the CRT function will be turned on in the CRT-OFF group and the CRT function will be turned off in the CRT-ON group in a cross-over design. All participants will cross-over at the 6-month follow-up visit. At 12-month follow-up, when each patient completes his/her cross-over 6-month therapy, the CRT function will be programmed on to provide chronic benefit from CRT for a battery life of 8.6 years. The subjects will be blinded from whether biventricular pacing is on or off. For participants who receive a CRT-D, the defibrillation function will be programmed on for the duration of the study.

Study device

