Peripheral venous blood samples will be collected before CRT, at 6-month and 12-month follow-up (either CRT-ON for 6-month or CRT-OFF for 6-month). At implant, blood samples from femoral artery and coronary sinus will be collected to measure transcardiac metabolomic gradient. More often, the LV lead deliver sheath for coronary sinus cannulation is able to be advanced into the beginning of lateral vein to facilitate the LV lead placement (70%-80%), where blood sample will be collected to determine the regional metabolic profile as shown in **Figure 12**. The rational for collecting the regional blood is to determine 1) whether there is a differential metabolisms between ICM (discrete scar vs no scar accessed by echocardiography) vs NICM (diffused fibrosis), and 2) metabolic feature at the most delayed conduction area at the LV lateral wall in coping with QRS-LV time.

Muscular samples collection for metabolomics measurement

When the patient is undergoing a CRT device implant, a pre-pectoral pocket is made routinely to house the generator. The skin and subcutaneous planes are dissected to expose the fascia of the pectoralis major. A small piece (0.5-1.0g) of the chest muscle (Pectoralis major) biopsy will be taken for metabolomics analysis, and mitochondrial physiology. Approximately 100mg of muscle tissue will be immediately used to evaluate mitochondrial capacity and bioenergetic efficiency using high-resolution respirometry and spectrofluorometry, as we have described previously [sup 1,2]. The remainder of the muscle tissue will be immediately blotted, frozen in liquid nitrogen, and stored at -80 C. Muscle mitochondrial content will be evaluated by laboratory-based enzymatic assays, protein expression, and mRNA abundance [sup 3]. Mass spectrometry and NMR spectroscopy will be used to detect and quantitate metabolites in muscle tissue lysates [sup 4]. Muscle biopsy may cause bleeding. We will use readily available cautery to stop the bleeding.

Device programming and follow-up

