Device pacing settings will be programmed in the DDDR mode at 60 to 150 beats/minutes. The CRT-ON or CRT-OFF will be programmed according to the randomization. Patients will be called at 1-month to evaluate for potential pocket discomfort and procedure-related complications. Patients will return for follow-up at 6-month (initial program CRT-ON or CRT-OFF) and 12-month (cross over program CRT-ON or CRT-OFF). Peripheral blood will be drawn for metabolomic study, and echocardiography, 6-minute walk, KCCQ, and NYHA class will be assessed at each follow-up. Patients will undergo standard clinical care to maximize CRT response. Device function will be closely monitored on a daily basis via a remote monitoring system. Patients will continue a stable medical therapy through entire study to minimize confounding due to drug changes during the study. Any adjustment in medications, if clinically needed, will be carefully recorded and we will take into consideration the confounding drug effect in analysis. After patients complete the study, they will be followed annually by phone to assess adverse events.

Schedule of Events

	Screening (within 90 days of implant)	Device Implant (Day 0 ± 4 days)	Post- Implant (Day 0 ± 4 days)	1 Month Phone Call (± 7 days)	6 Month (±30 days)	7 month (± 7 days)	12 Month (± 30 days)	24, 36, & 48 Month Phone Calls (± 30 days)
Echocardiogram (may include 3D echo imaging)	X ²				x		х	
Physical exam	х				х		х	
12-Lead ECG	х		х					

Six-minute walk test	х				х		х	
Kansas City Cardiomyopathy Questionnaire (KCCQ)	х				х		х	
Chest X-ray			Х					
Pregnancy test (if applicable)	X ¹							
Blood collection For biomarker analysis	Х	x			х		х	
Device programming/ interrogation			x		Х		Х	
SAE/AE Assessment (heart failure symptoms, pocket pain, device function, etc.)			x	х	х	х	х	х
Medication Reconciliation	Х		х	х	Х	х	х	

1. Females of child-bearing potential must have a negative pregnancy test within 7 days of device implant.

2. Imaging can be done within 12 months of implant.

Metabolomic analyses

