b. Amino acids are important substrates for energy production in the heart. Through a series of reactions, branched-chain amino acids (BCAAs) can be converted to metabolic intermediates and fed into the tricarboxylic acid (TCA) cycle as potential sources of anaplerotic input (Figure 14, red box). Due to the down regulation of gene expression related to the BCAA degradation and utilization, specifically, valine, leucine and isoleucine are accumulated in HF.^{53,81,82} Our preliminary data (shown in Figure 6 and 10), showed that the level of these BCAAs were disturbed even in mild HF and was significantly lower in CRT non-responders than in CRT responders with severe HF. Further, amino acids are not only cell building blocks, energy source and signaling molecules but are also regulators of gene expression and protein synthesis. Taken together, the BCAAs are critical metabolite markers in HF.

c. Using the new technology of whole blood ¹⁸O metabolic labeling, we will test the hypothesis that the 2,3-BPG[¹⁸O] and G-3-P[¹⁸O] turnover rates are reduced, while inorganic phosphate (Pi[¹⁸O]) and γ -ATP[¹⁸O] are elevated in mild LV dysfunction in which the impaired O2 and substrate transport and ATP synthesis may precede the HF symptoms (Figure 13).

d. We will develop strong metabolic biomarkers as proposed in above to determine the prognostication with clinical outcomes in patients with mild HF.

Primary clinical efficacy objective

The study primary endpoint is a reduction in the LV end-systolic volume index (LVESVI, reverse LV remodeling) in the CRT-ON group as compared to CRT-OFF group.

Secondary clinical efficacy objectives (composite events)

 Hospital admission for HF; 2) Increase in NT pro-BNP level by 30% and its predictive value of response to CRT; 3) Sustained ventricular tachycardia or fibrillation greater than 30 seconds; 4) Decrease in LVEF to ≤35%; and 5) death.

The analytical imprecision of natriuretic peptides depends on the assay but for NTprpoBNP it is roughly 1.6%. Inter and intradividual variation is roughly 30% (American Journal of Cardiology. 92(5):628-31, 2003). Thus values above 30% have been suggested to define significant changes in natriuretic peptides (Journal of Investigative Medicine. 61(6):950-5, 2013 Aug,). This value was shown to have prognostic significance in the VALHEFT trial (Journal of the American College of Cardiology. 52(12):997-1003, 2008 Sep 16) and thus will provide an end point in our proposed analysis.

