Primary safety objectives

Freedom from system-related complications in randomized participants will be calculated at 1, 6, and 12 months post-implant to determine the safety profile, including the device pocket hematoma, pneumothorax, myocardial perforation, lead dislodgment, lead revision, and device-related infection. This safety profile will be balanced against efficacy to quantify the risk-benefit ratio. This analysis will occur when all subjects have completed study procedures.

Sample Size Considerations and Statistical analysis

The timing of primary endpoint analysis will occur when all subjects have completed study procedures. The primary endpoint for Aim 1 is the change in LVESVI. We propose a paired t-test, which combines both

randomized groups together (n=50 + 50 = 100), and compares the CRT-ON condition to the CRT-OFF condition. The power can be estimated based on REVERSE (LVEF \leq 40%) showing a mean change of -18.4 +/- 29.5 ml/m2. Let us assume that in the current mildly impaired EF group, the reduction will be, not -18, but -12. Assuming the SD is 26, the power for the one-sample paired t-test is over 99%. If we assume an 80% attrition (n=40 + 40), the detectable difference with 80% power is 8.3 ml/m2, less than half of that observed in REVERSE. A secondary analysis will be a generalized linear model in which baseline, period 1, and period 2 values of LVESVI will be analyzed together, with the possibility of an order effect. If no order effect is detected, then the analysis will amount to the paired t-test already described. Data may be missing due to the occurrence of interim events. This would mean that the data are not missing at random. We propose to accommodate this by a rank-based procedure, in which the ON-OFF differences are ranked in both groups together. As a secondary endpoint, we will analyze the composite clinical endpoint described above. This endpoint will be analyzed as the time to the first of any of these component events. The crossover design can be accommodated by fitting the treatment variable ON-OFF as a time dependent binary variable that is 1 (ON) or 0 (OFF). Order effects can be accommodated by including interactions with time-period in the model.

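### Two components of the secondary composite are scheduled only at the visits around which programming switches, so a visit-dated Cox model with a time-dependent ON/OFF term moves the hazard ratio modestly towards 1 and loses power; a grouped-time analysis avoids this cheaply.

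*Combined protocol and SAP*

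**What the plan says.** The protocol's section on secondary clinical efficacy objectives lists five component events. Three can be dated to the day: HF admission, "Sustained ventricular tachycardia or fibrillation greater than 30 seconds", and death. Two depend on a test: "Increase in NT pro-BNP level by 30% and its predictive value of response to CRT", and the LVEF fall in "Decrease in LVEF to ≤35%; and 5) death". (The Study Overview gives 34% or lower for LVEF; that is a separate discrepancy to reconcile.)

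On test timing, the blood sampling section says "Peripheral venous blood samples will be collected before CRT, at 6-month and 12-month follow-up". The device follow-up section says "Peripheral blood will be drawn for metabolomic study, and echocardiography, 6-minute walk, KCCQ, and NYHA class will be assessed at each follow-up", with returns at 6 and 12 months. The Schedule of Events gives "6 Month (±30 days") and the same window at month 12. The design section says "All participants will cross-over at the 6-month follow-up visit".

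The statistical section analyses time to the first component event and handles the crossover by "fitting the treatment variable ON-OFF as a time dependent binary variable that is 1 (ON) or 0 (OFF"). It adds that order effects can be dealt with through interactions with time period. It does not name Cox regression for this analysis; the Study Overview and the metabolomics analysis section name it for the clinical endpoint. Nothing states how a visit-detected event is dated, which setting it is credited to, whether the switch is coded at its actual or nominal date, or how ties are handled.

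**The concern.** A visit-detected event becomes visible on the day the setting changes. Start-stop coding can still give the event the right setting, but the comparison group that day is the difficulty. Patients seen earlier in the 60-day window have already switched. They stand in the risk set under the opposite setting and cannot show a scheduled visit-detected event until month 12. More patients who started ON pass their 6-month visit event-free, so more of them sit in these risk sets labelled OFF. That dilutes the OFF event rate more than the ON rate and pulls the hazard ratio towards 1.

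What is at stake is the size of the estimated CRT effect on the clinical composite, and the chance of detecting it with at most 100 first events.

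**Working it through.** The plan gives no hazard ratio, event count or power for the composite, so there is no figure to reproduce; its power statement concerns LVESVI.

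**Inputs from the protocol.** n=100, allocation 1:1; visits at 6 and 12 months, ±30 days; switch at the 6-month visit.

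**Assumptions.** Visit-detected risk per period 20% ON and 35% OFF; dated events 5% (ON) and 7% (OFF) per year; visits uniform within the window; visit-detected events credited to the setting before the switch; Efron ties; two-sided 5% level (the plan states none).

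**Step 1: true hazard ratio.** Six-month cumulative hazard H = −ln(1 − p) + r/2.
- ON: 0.223 + 0.025 = 0.248
- OFF: 0.431 + 0.035 = 0.466
- Ratio: 0.248/0.466 = 0.53

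**Step 2: simulated trials.**

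| Model | Median HR | Power | Rejection under no effect |
|---|---|---|---|
| Cox, ON/OFF only | 0.62 | 35–37% | 2.5–3.4% |
| Cox, stratified by period | 0.58 | 44% | 5.2% |
| Grouped complementary log-log, ON/OFF and period | 0.53 | 59–60% | 5.9–6.0% |

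Further runs of 500 trials gave 35% and 38% power for the first model, and 58% and 60% for the third.

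**Step 3: where the shift comes from.** Stratifying by period removes the mixed risk sets and takes 0.62 to 0.58, about a third of the shift. The rest arises because visits spread over the window make Cox treat each visit event as having its own time, so the estimate approaches the ratio of per-period risks: (1 − e^−0.248)/(1 − e^−0.466) = 0.220/0.372 = 0.59. With all visits on one day, Cox gives about 0.535–0.54, with 57% power against 59% for the grouped model. Both parts therefore come from the visit window.

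**Step 4: lower risks.** At 10% ON and 17% OFF the true ratio is (0.105 + 0.025)/(0.186 + 0.035) = 0.59. Cox gives about 0.62–0.63 against 0.60 for the grouped model; power is about 19–23% against 27–31%.

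**Step 5: chance NT-proBNP rises.** The protocol puts NT-proBNP variation at roughly 30%, the same size as the event threshold. If that is within-patient variation (an assumption), about 26% of visits show a 30% rise by chance in either state. Adding an illustrative LVEF risk of 4% ON and 8% OFF, with −ln(1 − 0.26) = 0.301:
- ON: 0.301 + 0.041 + 0.025 = 0.367
- OFF: 0.301 + 0.083 + 0.035 = 0.419
- Ratio: about 0.87

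Cox gives 0.90, and power is at most 7% under either model.

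**Step 6: a second set of assumptions.** With true HR 0.6, 80% of the hazard visit-detected, and OFF six-month risk of 20/30/45%:
- Cox, setting before the switch, actual switch date: HR 0.63/0.63/0.67, power 18/25/26%
- Grouped model: HR 0.60/0.58/0.59, power 24/40/50%
- Cox, switch coded at nominal day 183: HR 0.79/0.80/0.82, power 8/10/11%
- Cox, event credited to the new setting: HR 0.95/0.96/0.98, power 3–4%

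At n=2,000 and 30% risk the first coding still gives 0.64, so this is bias and not small-sample noise. At 10% OFF risk it shows almost no shift (median HR 0.60).

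**The case against.** **The plan already allows a period term.** This is a fair point: comparing the grouped model only with Cox on ON/OFF alone overstates the gap. With period in the model, Cox gives about 0.58, and its rejection rate under no effect is close to nominal. It still has 44% power against 59%, so the period term recovers only part of the loss.

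**Part of the remaining gap is scale.** This also stands. Period-adjusted Cox lands close to the per-period risk ratio of 0.59, whereas 0.53 is the hazard ratio on the complementary log-log scale. The power comparison is not exactly matched for size either (5.2% against 5.9% under no effect), but 0.7 points does not explain 15 points of power.

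**The text does not force the faulty analysis.** The statistical section says what can be fitted and names no Cox model there. A grouped-time model with ON/OFF and period would be compatible with it. The point is therefore conditional on visit dating and Cox.

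**Low power exists anyway.** At HR 0.6, 80% power needs about 121 events (Schoenfeld: 4 × (1.96 + 0.84)²/(ln 0.6)²), and at most 100 first events are possible. The study is labelled a pilot and the endpoint is secondary. This limits the importance of the point but does not justify discarding further information.

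**Stronger readings that the documents do not support.**
- A reader might infer that tied event times cause the distortion. With all visits on one day, where ties are heaviest, Efron handling leaves almost no loss.
- A reader might infer that the visit-detected components are the commonest. The preliminary LBBB cohort shows 17% LVEF deterioration at one year, and the cited background gives HF hospitalisation of 5.7–7.2% a year. These are different cohorts, and no NT-proBNP event rate is given. Unscheduled echocardiograms or blood tests are not excluded either.
- A reader might infer that the effect will be nearly erased. That requires nominal-date or new-setting coding, which the plan neither states nor rules out.

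**Conclusion.** The point holds in a limited form. If NT-proBNP and LVEF events are dated at the visit and fitted in a Cox model with a time-dependent ON/OFF term, the protocol's ±30-day window moves the hazard ratio modestly towards 1 and costs power. At assumed risks of 20% and 35% the shift is from about 0.53 to about 0.62 without a period term, or 0.58 with one; power is 35–37% or 44%, against 59–60% for a grouped analysis. At 10% and 17% the shift in the hazard ratio is small and the power difference is about 8 points. If chance NT-proBNP rises dominate both states, no model gains.

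The event rates, visit-detected share and significance level are assumptions. It would go too far to say that a time-dependent treatment term is invalid, or that this trial would gain some 25 points of power: the documents give no component rates that support that scenario. The error is conservative and does not create false positive claims. This is a worthwhile, cheap improvement to a secondary endpoint.

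**What to change.** State in the statistical section that a visit-detected event is credited to the period that closes at that visit, that is, to the setting in force before the switch. Analyse the composite in grouped time (first event in period 1, in period 2, or none) with a complementary log-log model containing ON/OFF and period, tested by likelihood ratio. The ON/OFF coefficient keeps its hazard-ratio interpretation. Keep the time-dependent Cox model, with actual switch dates and a period term, for HF admission, VT/VF and death.

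The cost is some SAP wording and a few lines of code, with no new data or visits. The downside is that the exact days of dated events are not used in the composite.

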Metabolic Mapping and Cardiac Resynchronization (Aim 1)

NCT# 03420833

June 20, 2021

STUDY OVERVIEW

Title	Metabolic Mapping and Cardiac Resynchronization (Aim 1)						
Running Title	Metabolic Mapping and CRT						
IRB Protocol Number	17-003359						
Phase	Pilot						
Principal	[name]						
investigator	Mayo Clinic						
Objective	To determine early alterations in metabolic pathways and metabolomics biomarkers in patients with mild heart failure (HF) and left bundle branch block (LBBB), and their role in the prediction of outcomes by early CRT.						
Study Design	Single-center, randomized cross-over study						
Overall Study Design	We plan to complete subject enrollment by the end of Year 3. Data validation, adjudication and analysis will be finished by the end of Year 5.						
Subject Participation Duration	Approximately 12 months						
Primary	Primary efficacy objectives (composite endpoint)						
Objectives	The study primary endpoint is a reduction in the LV end-systolic volume index (LVESVI, reverse LV remodeling) in the CRT-ON gorup as compared to the CRT-OFF group.						
	 Primary Safety Objective Freedom from system-related complications in randomized subjects will be calculated at 1, 6, and 12 months post implant to determine the safety profile, including the device pocket hematoma, pneumothorax, myocardial performation, lead dislodgement, lead revision, and device-related infection This safety profile will be balanced against efficacy to quantify the risk-benefit ratio. 						
Secondary	Secondary efficacy objectives						
Objectives	 Hospital admission for HF Increase in NT pro-BNP level by 30% 						
	 Increase in NT pro-вые level by 30% Sustained ventricular tachycardia or fibrillation greater than 30 seconds 						
	 Decrease in LVEF to ≤34% 						
	Death						
Device	BIOTRONIK Edora HF-T QP, or Ilivia HF-T QP DF4						
Number of Subjects	100 subjects (of these 30 will be female)						
Subject Inclusion	• LVEF 35%-50%						
Criteria	 NYHA class I-II QRS duration of ≥120ms 						
	Left bundle branch block (LBBB)						
	Patient is able to receive a transvenous pectoral CRT implant						

	 Patient is able to sign informed consent Two echocardiograms are required to confirm LVEF≤ 50% (one echo must be within 12 months of enrollment) Patient is on optimal and stable medical therapy (ACE inhibitor or AT1 blocker, beta blocker, etc. over the last 6 months)

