advanced HF (LVEF <35%) and 10 controls who underwent catheter ablation for supraventricular tachycardia. Blood samples were collected before and 3 months after the procedure. We performed a metabolomic profiling, using GC-MS and NMR. The plasma metabolomic profiles changed significantly 3 months after CRT (Figure 5A). For each patient with HF, scores of the integral metabolomic profile after CRT clustered separately from the original state on the orthogonal partial least squaresdiscriminant analysis (PLS-DA) plot, which

Protocol version 10 dated June 20, 2021

Figure 5. Metabolomic signature of heart failure (HF). (A) Changes in plasma metabolomic profile of HF patients and controls by orthogonal partial least squares discriminant analysis (OPLS-DA). CRT, cardiac resynchronization therapy. (B) Most important metabolites in the metabolomic signature of HF by variable importance in the projection (VIP). (C) Pattern of plasma metabolite changes in HF patients (n = 24; *P < .05; **P < .001). (D) Metabolic pathways most affected in HF as deduced from an altered plasma metabolomic profile.

indicates a transition to a new metabolic state. An integrated panel of the most important metabolites for discrimination of the CRT group included isoleucine, glutamine, and glycerol-1-phosphate (**Figure 5B**). The pattern of metabolite changes (decrease in succinate and increase in glutamate) indicated an improved mitochondrial substrate metabolism after CRT (**Figure 5C**). Among the most improved metabolic pathways were amino acid and lipid metabolism (**Figure 5D**).

Metabolomic profile in mild HF. We prospectively studied metabolomic profiles in subjects with a normal LVEF of >55% and LBBB (control, n=9), in patients with LVEF of 36%-50% and LBBB (HF mild, n=8), LVEF of ≤35% and LBBB before (HF severe, n=9) and after CRT (HF-CRT). Figure 6 illustrates the power of metabolomics in different HF stages separating from the control group. The most important metabolites in the discrimination of HF severity were amino acids (asparagine, lysine, glutamine), branched-chain amino acids (isoleucine, leucine, valine) and products of catabolism. carnitine and nucleotide degradation. The finding suggests an early alteration and progression in the amino acid, fatty acid and nucleotide metabolism in mild HF with LBBB in parallel to the advancement of HF.

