Metabolomic profile predicts improvement in LVEF after CRT. Of the 24 patients with HF who received CRT, 10 (41%) had an improvement in LVEF by >5% and a decrease of 1 or greater in the New York Heart Association (NYHA) functional class; they were considered to be CRT responders. This group of patients differed in their pre-CRT baseline plasma metabolomic profile from nonresponders in the orthogonal PLS-DA plot analysis (Figure **10A**). The panel of the most important metabolites allowing distinction between responders and non-responders to CRT is shown (Figure 10B). Patients who responded to CRT had higher levels of branched-chain amino acids (isoleucine, leucine, and valine), essential for protein synthesis and metabolic signaling. (Figure 10C; P<.05). It indicates branched-chain amino acids are catabolized to metabolic intermediates as important substrates for energy production in the failing heart.

CRT and gender difference

Figure 10. Metabolomic profiles of responders and nonresponders to cardiac resynchronization therapy (CRT). (A) Distinction of basal plasma metabolomic profiles of responders and nonresponders to CRT by orthogonal partial least squares discriminant analysis (OPLS-DA). (B) An integral panel of the most important metabolites permitting prediction of responders by variable importance in the projection (VIP). (C) A panel of the most important metabolite differences between responders and nonresponders (*P < .05).

Women have a greater response to CRT than men. We conducted a retrospective study of 728 consecutive CRT recipients at our institution who met the guidelines for CRT-D device placement. The outcomes of CRT were compared between women (n=166, 22.8%) and men (n=562, 77.2%). Women were found to more often have NICM (68% vs 36%, P<.01). After CRT, as compared to men, women had a greater improvement in the NYHA class and a trend greater improvement in LVEF and reverse LV remodeling.⁶²

Women and men with HF have different metabolomic profiles. The metabolomic profile was prospectively studied in 38 patients (7 women, 18%) who had advanced HF with LVEF ≤35%. Male and female patients had different plasma metabolomic profiles (Figure 11A). Women had higher plasma levels of linoleic acid, palmitoleic acid, glycolic acid and glycine, which indicated a better lipid and amino acid metabolism than men (Figure 11B). A distinct feature of the female metabolome was а higher

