Metabolomics data analysis. The timing of metabolomics data analysis will occur when all subjects have completed study procedures. Data sets will be mean-centered and pareto-scaled to adjust the importance of high- and low-abundance metabolites to an equal level before carrying out statistical analyses. 42,52,77-79,84-86 The SIMCA-P+ 12.0 software package (Umetrics, Umea, Sweden) will be used for pattern recognition multivariate analysis, including unsupervised principal component analysis (PCA), supervised partial least squares discriminant analysis (PLS-DA), and orthogonal partial least-squares discriminant analysis (OPLS-DA). The data will be examined with PCA scatter plot of the first two score vectors (t1-t2) in order to reveal the homogeneity of the data, any groupings, outliers, and trends. Then PLS-DA is applied to increase the class separation, simplify interpretation, and find potential biomarkers. The OPLS-DA will be used to identify the significantly different metabolites between groups. For validation, R2 (the fraction of variance explained by a component) and Q2 (the fraction of the total variation predicted by a component) values will be considered as measures of goodness of model and the model robustness, respectively. The value of Q2 ranges from 0 to 1 and typically a Q2 value of greater than 0.4 is considered a good model. Most important metabolites will be selected according to the variable importance in the projection (VIP) values and the variables with VIP>1 will be considered for significantly changed metabolites. Metabolic pathway analysis will be performed using MetaboAnalyst 3.0 software.⁸³ In addition, we will explore the new multivariate metabolomics data (80 variables on 80 subjects), and construct principal components agnostically using SAS PROC FACTOR. Preliminary data suggest that 5 to 10 factors will represent 60% or more of the joint variation among the 80 metabolites. The 5-10 factors will then be calculated on each subject, and used to predict group differences (using a two-sample t-test), and response to CRT therapy. In particular, we will then relate these principal components (PC's) to response to CRT using multiple linear regression (for the LVESVI endpoint) and Cox Regression (for the Clinical endpoint).

Safety and Adverse Events

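### Metabolites are called significantly changed on VIP>1, a relative ranking with no error rate, tied neither to the plan's Q2>0.4 benchmark nor to a test of each metabolite

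*Combined protocol and SAP*

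**What the plan says.** The Metabolomics data analysis section moves from PCA to PLS-DA to OPLS-DA. The last step is given an inferential task: "The OPLS-DA will be used to identify the significantly different metabolites between groups". R2 and Q2 are named as validation measures, with the remark that "typically a Q2 value of greater than 0.4 is considered a good model". The selection rule follows: "the variables with VIP>1 will be considered for significantly changed metabolites".

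The section does not say that VIP is read only when Q2 exceeds 0.4, or what happens when it does not. It plans no test, p-value or false discovery rate for a single metabolite. Its one two-sample t-test applies to the 5-10 factor scores. Pathway analysis comes next, and that does not confirm individual metabolites. Under Objectives of metabolomic measurements, item 3c announces a hypothesis on four labelled markers named in advance, without a test or level. No other section adds a condition to the VIP rule.

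**The concern.** The objective in the Study Overview opens "To determine early alterations in metabolic pathways and metabolomics biomarkers in patients with mild heart failure", and the background section on gender difference seeks a metabolomic signature of women that may differ from that of men. A list of significantly changed metabolites is therefore one of the study's intended products. Readers take that label to mean a bounded chance of error, whereas VIP>1 means only above-average weight within one fitted model.

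Two things follow from the text as written. A list can be drawn from a model that fails the plan's own benchmark. In a model that passes, nothing bounds the share of false entries.

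The preliminary work did show p-values beside VIP; panel C of Figure 10 is described as "A panel of the most important metabolite differences between responders and nonresponders (*P < .05". The analysis section does not carry that practice over as a rule, and the figure legends state no multiplicity control.

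**Working it through.** The plan gives no error rate or power for metabolite selection, so there is no figure of its own to reproduce.

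**Inputs from the documents.** 80 metabolites and 80 subjects (stated for the factor analysis, assumed here to apply to OPLS-DA as well); mean-centring and Pareto scaling; "5 to 10 factors will represent 60% or more of the joint variation among the 80 metabolites"; 30 women among 100 patients, so 0.30 × 80 = 24 women versus 56 men; all patients cross over, so CRT-ON versus CRT-OFF is paired.

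**Assumed inputs.** Number of metabolites truly changed; effect size; spread of metabolite SDs (log-normal); correlation (none, or 7 factors explaining 60%); 0 or 1 orthogonal component; within-patient correlation of 0.5 and no period effect for the paired design; 7-fold Q2.

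**1. Algebra.** On the single predictive component, VIP_j = √p × |w_j| with Σw_j² = 1. Hence mean VIP² = (1/p) × Σ p·w_j² = 1. Unless all VIPs are equal, at least one exceeds 1 whatever the data. With equal variances and no group difference, VIP² behaves roughly as chi-square with 1 df: P(χ²₁ > 1) = 0.317, and 80 × 0.317 = 25.4 metabolites.

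**2. Nothing changed (simulated, 24,000 runs).** For 40 vs 40 and uncorrelated metabolites, VIP>1 flagged on average 25.9, 23.6, 19.2 and 12.1 of 80 as the log-SD spread rose through 0, 0.5, 1 and 2. With 7 factors the averages were 26.7, 24.2, 19.7 and 12.2. The 24 vs 56 and paired designs were within 0.2 of these. The largest Q2 was 0.28, so Q2>0.4 was met in 0 of 24,000 runs.

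**3. Some metabolites changed by 0.8-1.0 SD, models passing Q2>0.4.** Mean false share of the VIP>1 list:

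| Truly changed, of 80 | Independent groups (40 vs 40 or 24 vs 56) | Paired ON/OFF |
|---|---|---|
| 5 | 56-76% | 21-38% |
| 10 | 29-47% | 0-22% |
| 20 | 5-23% | 0-3% |
| 30 | 1-13% | 0-1% |

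Per-metabolite tests with Benjamini-Hochberg at 5% give about 0-8% throughout. These ranges are approximate, and with 5 changed few models may pass.

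One setting with 10 changed (40 vs 40, 7 factors, equal SDs, 0.8 SD, 1 orthogonal component): 98% of models pass. The VIP>1 list averages 9.8 true and 8.0 false entries, 8.0/17.8 = 45% false. Benjamini-Hochberg at 5% averages 7.6 true and 0.4 false, 0.4/8.0 = 5%.

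The documents do not say which VIP version will be read. With 10 changed, a two-component PLS-DA VIP gives higher shares: 35-57% independent, 3-44% paired.

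**4. Would an uncorrected p<0.05 be enough?** Under the null it flags 80 × 0.05 = 4 metabolites on average, and the chance of at least one is 1 − 0.95⁸⁰ = 98.3% if the tests are independent. With 10 changed, requiring both VIP>1 and p<0.05 still leaves 12-29% false in independent groups and 1-8% in the paired contrast.

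**The case against.** The strongest reply has four parts.

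- *The wording describes a shortlist.* 'Considered for' can be read that way, with 'significantly' as loose language. But a shortlist needs a later confirming step, none is planned, and OPLS-DA has just been given the task of identifying significant differences.
- *Q2 already validates the model.* It is introduced for validation just before the VIP sentence, and no null run reached 0.4. A reader might infer from step 2 that the trial will report lists drawn from pure noise. That is not supported: it would require the team to disregard its own benchmark. What stands is that the text does not make Q2 a condition, and that Q2 judges the model, not each entry.
- *The false share is not known.* A reader might infer that a third to a half of any list will be false. That holds only near 10 changed of 80, a number found nowhere in the documents. With 20 or 30 changed the share is much smaller; with 5 it is larger.
- *The main contrast is paired, and this is a pilot.* Both are true. For CRT-ON versus CRT-OFF, VIP>1 is often no worse than Benjamini-Hochberg. The women-versus-men comparison remains independent, and there the shares are higher.

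These replies narrow the point considerably but do not remove it.

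**Conclusion.** The point holds as a minor defect in an exploratory analysis. A label that implies significance rests on a cut-off without an error rate, and the two safeguards that could support it are respectively unenforced and absent. The algebra needs no assumption. The sizes rest on assumed SDs, correlations and effects, and above all on the unknown number of truly changed metabolites, so they show a range and do not predict this trial's result.

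A reader might infer that the trial's main conclusion is at risk. It is not: the LVESVI endpoint, the markers named in advance and the factor-based regressions do not use the VIP rule.

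**What to change.** State in the analysis section that VIP is a descriptive ranking, read only from models that meet the plan's own Q2>0.4. Call a metabolite significantly changed only if it passes a per-metabolite test with Benjamini-Hochberg control at a pre-stated level, such as 5%, or 10% if the team prefers more yield in a pilot. Use a paired, period-adjusted test for CRT-ON versus CRT-OFF and a two-sample test for independent groups. If no such test is added, drop 'significantly' and call the VIP>1 list candidates.

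The change needs wording and a short script on data already planned. It does cost yield when effects are weak and groups independent. At 0.5 SD, in models passing Q2>0.4, Benjamini-Hochberg at 5% labels about 5-8 true metabolites against 12-16 for VIP>1 with 20 truly changed, and about 8-11 against 15-22 with 30. The Q2 condition does not make this loss moot. With 10 changed at 0.5 SD (40 vs 40) at most 4% of models pass, but with 20-30 changed between 6% and 100% do. The metabolites that lose the label stay visible in the VIP ranking.
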